#### 12.4.2 Serious Adverse Event (SAE)

Information about all serious adverse events will be collected and recorded. A serious adverse event is an undesirable sign, symptom or medical condition which:

- is fatal or life-threatening
- results in persistent or significant disability/incapacity
- is medically significant, i.e., defined as an event that jeopardizes the patient or may require medical or surgical intervention to prevent one of the outcomes listed above
- causes congenital anomaly or birth defect
- requires inpatient hospitalization or prolongation of existing hospitalization, unless hospitalization is for:
  - routine treatment or monitoring of the studied indication, not associated with any deterioration in condition (procedures such as central line placements, paracentesis, pain control)
  - elective or pre-planned treatment for a pre-existing condition that is unrelated to the indication under study and has not worsened since the start of study treatment
  - treatment on an emergency outpatient basis for an event not fulfilling any of the definitions of a SAE given above and not resulting in hospital admission
  - social reasons and respite care in the absence of any deterioration in the patient's general condition

Protocol name: NOVEMBER (Novem- (9), BrEast Radiation), A Phase II trial of a 9 day course of whole breast radiotherapy for early stage breast cancer.

Version Date: 23NOV2021

Principal Investigator: [name]

Serious adverse events will be recorded after the start of radiation therapy until year 3.

Any death from any cause while a patient is receiving treatment on this protocol or up to 30 days after the last dose of protocol treatment, or any death which occurs more than 30 days after protocol treatment has ended but which is felt to be treatment related, must be reported.

Toxicities which fall within the definitions listed above must be reported as an SAE regardless if they are felt to be treatment related or not. Toxicities unrelated to treatment that do NOT fall within the definitions above, must simply be documented as AEs in the patient research chart.

## **12.5 SAE Reporting Requirements**

SAEs must be reported to the DSMC, the FDA, and the IRB, according to the requirements described below:

A MedWatch 3500A form must be completed and submitted to [[contact]](mailto:[contact]) as soon as possible, but no later than 1 business day of first knowledge or notification of event.

### DSMC Notifications:

- An HCI Research Compliance Officer (RCO) will process and submit the MedWatch form to the proper DSMC member as necessary for this study.
- The RCO will summarize and present all reported SAEs according to the Data and Safety Monitoring Plan at the quarterly DSMC meeting.

### FDA Notifications:

- Adverse events occurring during the course of a clinical study that meet the following criteria will be promptly reported to the FDA:
  - Serious
  - Unexpected
  - Definitely, Probably or Possibly Related to the investigational treatment.
- Fatal or life-threatening events that meet the criteria above will be reported within 7 calendar days after first knowledge of the event by the investigator; followed by as complete a report as possible within 8 additional calendar days.
- All other events that meet the criteria above will be reported within 15 calendar days after first knowledge of the event by the investigator.
- The RCO will review the MedWatch report for completeness, accuracy and applicability to the regulatory reporting requirements.
- The RCO will ensure the complete, accurate and timely reporting of the event to the FDA.

Protocol name: NOVEMBER (Novem- (9), BrEast Radiation), A Phase II trial of a 9 day course of whole breast radiotherapy for early stage breast cancer.

Version Date: 23NOV2021

Principal Investigator: [name]

- The MedWatch report will be submitted to the FDA through the voluntary reporting method by the Regulatory Coordinator.

**IRB Notification:**

- Events meeting the University of Utah IRB reporting requirements will be reported per local guidelines within 10 working days.
- \*MedWatch 3500A form can be found on line at the FDA website.

**12.6 Reporting of Pregnancy**

Although pregnancy is not considered an adverse event, it is the responsibility of investigators or their designees to report any pregnancy or lactation in a subject, including the pregnancy of a male subjects' female partner as an SAE. Pregnancies or lactation that occurs during the course of the trial or with 30 days of completing the trial or starting another new anticancer therapy, whichever is earlier, must be reported to the DSMC, IRB, FDA, and the sponsor as applicable. All subjects and female partners who become pregnant must be followed to the completion/termination of the pregnancy. Pregnancy outcomes of spontaneous abortion, missed abortion, fetal death, intrauterine death, miscarriage and stillbirth must be reported as serious events.

**12.7 Protocol Amendments**

Any amendments or administrative changes in the research protocol during the period, for which the IRB approval has already been given, will not be initiated without submission of an amendment for IRB review and approval.

These requirements for approval will in no way prevent any immediate action from being taken by the investigator in the interests of preserving the safety of all patients included in the trial.

**12.8 Protocol Deviations**

A protocol deviation (or violation) is any departure from the defined procedures and treatment plans as outlined in the protocol version submitted and previously approved by the IRB. Protocol deviations have the potential to place participants at risk and can also undermine the scientific integrity of the study thus jeopardizing the justification for the research. Protocol deviations are unplanned and unintentional events.

Because some protocol deviations pose no conceivable threat to participant safety or scientific integrity, reporting is left to the discretion of the PI within the context of the guidelines below. The IRB requires the **prompt reporting** of protocol deviations which are:

- Exceptions to eligibility criteria.
- Intended to eliminate apparent immediate hazard to a research participant or
- Harmful (caused harm to participants or others, or place them at increased risk of harm - including physical, psychological, economic, or social harm), or

Protocol name: NOVEMBER (Novem- (9), BrEast Radiation), A Phase II trial of a 9 day course of whole breast radiotherapy for early stage breast cancer.

Version Date: 23NOV2021

Principal Investigator: [name]

- Possible serious or continued noncompliance

## **12.9 FDA Annual Reporting**

This study is IND exempt therefore there are no annual reporting requirements to the FDA.

## **12.10 Clinical Trials Data Bank**

The study will be registered on <http://clinicaltrials.gov> and the NCI CTRP (Clinical Trials Reporting Program) by the Clinical Trials Office.

## **12.11 Record Keeping**

Per 21 CFR 312.57, Investigator records shall be maintained for a period of 2 years following the date a marketing application is approved; or, if no application is filed or the application is not approved, until 2 years after the investigation is discontinued and the FDA is notified.

## **14 APPENDICES**

Appendix I: Breast-Q Breast Conservation Module

# **NOVEMBER**

## **BREAST-Q™- BREAST CONSERVING THERAPY MODULE (POSTOPERATIVE) 2.0**

**Patient Study ID:** 103976-01-\_\_\_\_\_

**Patient Initials:** \_\_\_\_\_

**Date of Completion:** \_\_\_\_\_ / \_\_\_\_\_ / \_\_\_\_\_

All applicable Breast Conserving modules should be completed at the indicated time points in the study calendar.

- Satisfaction with Breasts
- Adverse Effects of Radiation (to be completed post radiation only)
- Psychosocial Well-Being
- Physical Well-Being: Chest
- Sexual Well-Being

**BREAST-Q™ - BREAST CONSERVING THERAPY MODULE (POSTOPERATIVE) 2.0**  
**SATISFACTION WITH BREASTS**

The following questions are about your breasts and your breast cancer treatment (by treatment, we mean lumpectomy with or without radiation). If you have had a lumpectomy and radiation of both breasts, answer these questions thinking of the breast you are least satisfied with.

With your breasts in mind, in the past week, how satisfied or dissatisfied have you been with:

	Very Dissatisfied	Somewhat Dissatisfied	Somewhat Satisfied	Very Satisfied
a. How you look in the mirror clothed ?	1	2	3	4
b. The shape of your lumpectomy breast when you are wearing a bra?	1	2	3	4
c. How normal you feel in your clothes?	1	2	3	4
d. Being able to wear clothing that is more fitted?	1	2	3	4
e. How your lumpectomy breast sits/hangs?	1	2	3	4
f. How smoothly shaped your lumpectomy breast looks?	1	2	3	4
g. The contour (outline) of your lumpectomy breast?	1	2	3	4
h. How equal in size your breasts are to each other?	1	2	3	4
i. How normal your lumpectomy breast looks?	1	2	3	4
j. How much your breasts look the same?	1	2	3	4
k. How you look in the mirror unclothed ?	1	2	3	4

Protocol name: NOVEMBER (Novem- (9), BrEast Radiation), A Phase II trial of a 9 day course of whole breast radiotherapy for early stage breast cancer.

Version Date: 23NOV2021

Principal Investigator: [name]

## **BREAST-Q™ - BREAST CONSERVING THERAPY MODULE (POSTOPERATIVE) 2.0 ADVERSE EFFECTS OF RADIATION**

If you have had radiation on both breasts, answer these questions thinking of the breast you are least satisfied with.

With your radiated breast(s) in mind, in the past week, how much have you been bothered by:

	Not at all	A little	A lot
a. Your radiated breast skin looking different (e.g. too dark or too light)?	1	2	3
b. Marks on your breast skin caused by radiation (e.g. small visible blood vessels)?	1	2	3
c. Your radiated breast skin feeling dry?	1	2	3
d. Your radiated breast skin feeling sore (sensitive) when touched (e.g. changes in water temperature when you bathe/shower)?	1	2	3
e. Your radiated breast skin feeling unnaturally thick (rough, tough) when you touch it?	1	2	3
f. Your radiated breast skin feeling irritated by clothing that you wear?	1	2	3

Protocol name: NOVEMBER (Novem- (9), BrEast Radiation), A Phase II trial of a 9 day course of whole breast radiotherapy for early stage breast cancer.

Version Date: 23NOV2021

Principal Investigator: [name]

**BREAST-Q™ - BREAST CONSERVING THERAPY MODULE (POSTOPERATIVE) 2.0**  
**PSYCHOSOCIAL WELL-BEING**

With your breasts in mind, in the past week, how often have you felt:

	None of the time	A little of the time	Some of the time	Most of the time	All of the time
a. Confident in a social setting?	1	2	3	4	5
b. Emotionally able to do the things that you want to do?	1	2	3	4	5
c. Emotionally healthy?	1	2	3	4	5
d. Of equal worth to other women?	1	2	3	4	5
e. Self-confident?	1	2	3	4	5
f. Feminine in your clothes?	1	2	3	4	5
g. Accepting of your body?	1	2	3	4	5
h. Normal?	1	2	3	4	5
i. Like other women?	1	2	3	4	5
j. Attractive?	1	2	3	4	5

Protocol name: NOVEMBER (Novem- (9), BrEast Radiation), A Phase II trial of a 9 day course of whole breast radiotherapy for early stage breast cancer.

Version Date: 23NOV2021

Principal Investigator: [name]

**BREAST-Q™ - BREAST CONSERVING THERAPY MODULE (POSTOPERATIVE) 2.0**  
**PHYSICAL WELL-BEING: CHEST**

In the past week, how often have you experienced:

	None of the time	Some of the time	All of the time
a. Difficulty lifting or moving your arms?	1	2	3
b. Difficulty sleeping because of discomfort in your breast area?	1	2	3
c. Tightness in your breast area?	1	2	3
d. Pulling in your breast area?	1	2	3
e. Tenderness in your breast area?	1	2	3
f. Sharp pains in your breast area?	1	2	3
g. Aching feeling in your breast area?	1	2	3
h. Difficulty laying on the side of your lumpectomy breast?	1	2	3
i. Swelling of the arm (lymphedema) on the side(s) that you had your breast surgery?	1	2	3

Protocol name: NOVEMBER (Novem- (9), BrEast Radiation), A Phase II trial of a 9 day course of whole breast radiotherapy for early stage breast cancer.

Version Date: 23NOV2021

Principal Investigator: [name]

## **BREAST-Q™ - BREAST CONSERVING THERAPY MODULE (POSTOPERATIVE) 2.0 SEXUAL WELL-BEING**

Thinking of your sexuality, since your lumpectomy surgery, how often do you generally feel:

	None of the time	A little of the time	Some of the time	Most of the time	All of the time
a. Sexually attractive in your clothes?	1	2	3	4	5
b. Comfortable/at ease during sexual activity?	1	2	3	4	5
c. Confident sexually?	1	2	3	4	5
d. Satisfied with your sex-life?	1	2	3	4	5
e. Confident sexually about how your breast(s) look when unclothed ?	1	2	3	4	5
f. Sexually attractive when unclothed ?	1	2	3	4	5

Protocol name: NOVEMBER (Novem- (9), BrEast Radiation), A Phase II trial of a 9 day course of whole breast radiotherapy for early stage breast cancer.

Version Date: 23NOV2021

Principal Investigator: [name]

## Appendix II – Health Care Expense Survey

# NOVEMBER

## Health Care Expense Survey

**Patient Study ID:** 103976-01-\_\_\_\_\_

**Patient Initials:** \_\_\_\_\_

**Date of Completion:** \_\_\_\_\_ / \_\_\_\_\_ / \_\_\_\_\_

Protocol name: NOVEMBER (Novem- (9), BrEast Radiation), A Phase II trial of a 9 day course of whole breast radiotherapy for early stage breast cancer.

Version Date: 23NOV2021

Principal Investigator: [name]

### Health Care Expense Survey

Before you were diagnosed with breast cancer, did you do paid or unpaid work outside the home?

Yes     No

If you worked outside the home, which of the following best applies to you?

Paid work outside the home  Yes     No

Unpaid work outside the home  Yes     No (including work in a family farm or business).

Self-employed / business owner  Yes     No

If you worked outside the home:

How many days per week did you work? \_\_\_\_ (days)

How many hours per day did you work? \_\_\_\_ (hours)

What is your profession?

---

In what industry do you work?

---

What is / was your job title?

---

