For comparison assessment, this survey will be administered to an additional 45 patients undergoing standard of care hypofractionated radiation who are otherwise not eligible or interested in enrollment on this protocol. The Health Care Expense Survey should be provided to the patient and completed by the patient 2-8 weeks post standard of care hypofractionated radiation. The comparison group will either receive a \$20 meal card or be reimbursed for a meal up to \$20, with provision of a receipt from the date of the study visit, after completion of the Health Care Expense Survey. This comparison cohort will be case-matched for distance to treatment facility and employment status.

Collected 2-8 weeks after the completion of radiation:

- Work status prior to breast cancer diagnosis (job for pay or business owner, not including work around the house; including work in a family farm or business even if unpaid).

Protocol name: NOVEMBER (Novem- (9), BrEast Radiation), A Phase II trial of a 9 day course of whole breast radiotherapy for early stage breast cancer.

Version Date: 23NOV2021

Principal Investigator: [name]

- If working number of days working per week.
- If working, number of hours working per day.
- Profession and the job title.
- Total number of hours spent for each radiation treatment (time from leaving home or work to return to home or work).
- Distance from radiation treatment facility from home or work.
- Means of getting to radiation treatment facility (ask if only one modality used or a combination, if a combination record number of days for each modality).

1) Car

- Approximate cost for parking
- Did patient drive, was patient driven, or a combination

2) Shuttle

- Approximate cost

3) Public transportation

- Approximate cost per visit

4) Foot

5) Taxi/car service

- Approximate total cost per visit (both ways)

- Number of radiation treatments during which at least one other person accompanied patient

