### 9.2.4 Economic Analysis:

Cost-effectiveness (CE) analysis of hypofractionated radiation versus standard fractionation will be explored using cost data and quality adjusted life years (QALYs) (i.e. effectiveness side). A societal perspective will be applied for the analysis because the direct costs (i.e. resource used) relevant to treatments/intervention, indirect costs (i.e. resource lost such as travel time, lost productivity) and side-effects related costs will be considered. Cost for the intervention will be measured for the cost of therapy, medications, hospitalization and medical visits. Costs for treatments due to side effects will be collected. Patient times spent for treatment, travel and lost productivity will be converted to costs using year 2022 mean adult US wage rate. Because costs related to the intervention will be occurred in different years (for example, 2018~2022), they will be adjusted to year 2022 US dollars using the medical component of the Consumer Price Index. If charged amounts relevant to the treatments are available only (i.e. plan paid amounts or reimbursed amounts are not available), they will be converted to costs by using cost-to-charge ratios. We will not compare charges or costs between institutions. The quality of life (QoL) measures will be based on the BREAST-Q and EQ-5D survey and will be used to calculate Quality Adjusted Life Years (QALYs) for the effectiveness side. Because costs and effects will be measured over multiple years, both costs and effects will be discounted at the rate of 3.5%. We will utilize the EQ-5D and Breast-Q to assist in the QALY analysis. See appendix IV. Once parameters are computed: 1) mean differences in cost and effect between treatments, 2) variances for differences in costs and effects, and 3) covariance between effectiveness and cost difference, the incremental cost-effectiveness ratio (ICER) or incremental net benefits summarizing the monetary value of the intervention will be calculated.

$$ICER = \frac{Cost_{\text{Hypofractionated Radiation}} - Cost_{\text{Standard Fractionation}}}{Effect_{\text{Hypofractionated Radiation}} - Effect_{\text{Standard Fractionation}}}$$

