**NOTE: This section is designed to capture the out of pocket expenses associated with radiation therapy.**

How many hours were spent in total for each radiation treatment (time from leaving home/other accommodation or work to return to home/other accommodation or work)?

\_\_\_\_ (hours)

What is the distance from the radiation treatment facility from home/other accommodation or work? \_\_\_\_ (miles)

Did you commute daily to radiation treatment from your home?  Yes     No

Protocol name: NOVEMBER (Novem- (9), BrEast Radiation), A Phase II trial of a 9 day course of whole breast radiotherapy for early stage breast cancer.

Version Date: 23NOV2021

Principal Investigator: [name]

(If yes), method of transport used to get to the radiation therapy facility (Check all that apply)

Car  Yes  No

(If yes) approximate cost for parking per visit \$\_\_\_\_\_.\_\_\_\_

Did you drive yourself?  Yes  No

Were you driven?  Yes  No

Was it a combination of driving yourself or being driven  Yes  No

Shuttle  Yes  No

(If yes) Approximate cost per visit \$\_\_\_\_\_.\_\_\_\_

Public transport  Yes  No

(If yes) Approximate cost per visit \$\_\_\_\_\_.\_\_\_\_

On foot  Yes  No

Taxi/car service  Yes  No

(If yes) Approximate cost per visit (both ways) \$\_\_\_\_\_.\_\_\_\_

(If no), which of the follow apply (check one):

I was in a health care facility during radiation

I was living with a friend/family member during radiation (answer the commuting questions above)

I stayed hotel, apartment, or similar facility during radiation (answer the commuting questions above)

If hotel, apartment or similar facility, estimated cost of lodging during your radiation treatment \$\_\_\_\_\_.\_\_\_\_

Number of radiation treatments during which at least one other person accompanied patient \_\_\_\_

Number of visits to radiation treatment facility since completing radiation therapy (follow up visits) \_\_\_\_

Protocol name: NOVEMBER (Novem- (9), BrEast Radiation), A Phase II trial of a 9 day course of whole breast radiotherapy for

early stage breast cancer.

Version Date: 23NOV2021

Principal Investigator: [name]

From the 1st day of starting radiation, until 40 days after the completion of radiation:

Number of days the patient was unable to go to work at all \_\_\_\_

Number of days the patient went to work part-time \_\_\_\_

If part time, number of hours reduced from typical work day \_\_\_\_

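### The expense survey limits work to work outside the home, a limit section 8.4 does not set, so a patient who earned only at home gives no hours with which to cost her full days lost

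*Combined protocol and SAP*

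**What the plan says.** Section 8.4 (Economic Analysis) lists what the survey collects 2 to 8 weeks after radiation. The first item is work status before diagnosis, defined as "job for pay or business owner, not including work around the house; including work in a family farm or business even if unpaid". It says nothing about where the work is done. The same section has the survey completed by 45 additional patients on standard hypofractionated radiation, and says: "This comparison cohort will be case-matched for distance to treatment facility and employment status".

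The form in Appendix II (Health Care Expense Survey) begins: "Before you were diagnosed with breast cancer, did you do paid or unpaid work outside the home". The next block is headed "If you worked outside the home, which of the following best applies to you" and has three separate Yes/No lines: paid work, unpaid work (with family farm or business in brackets), and "Self-employed / business owner". Days per week, "How many hours per day did you work", profession, industry and job title follow under the same outside-the-home condition.

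Later items do not carry that condition. They ask for "Number of days the patient was unable to go to work at all", days worked part-time, hours reduced on those days, and wages lost.

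Section 9.2.4 states the valuation: "Patient times spent for treatment, travel and lost productivity will be converted to costs using year 2022 mean adult US wage rate".

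**The concern.** Section 8.4 excludes a kind of activity, housework. The form excludes a place, the home. The two rules classify some patients differently, and the form is the only employment record that the protocol describes; the study calendar lists no other.

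Indirect patient cost is part of a named secondary objective (section 1.2.4), and section 8.4 expects shorter treatment to mean less time off work. Work status and usual hours feed that quantity. If a group of earners is recorded as not working, their missed days lack the hours needed to cost them. Employment status is also one of the two matching factors for the comparators, so its definition should not depend on how a patient reads one phrase.

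**Working it through.** The plan states no figure to reproduce. The check sets the definition beside the form and follows each type of patient through to the costing.

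**Step 1. Classification.**

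| Patient before diagnosis | Section 8.4 | Appendix II, read literally |
|---|---|---|
| Paid, works at an employer's site | Working | Yes; days, hours and occupation recorded |
| Paid, works partly at home and partly elsewhere | Working | Yes; recorded |
| Paid, works only at home | Working | No; days, hours and occupation skipped |
| Owner of a business run only from home | Working | No; the self-employed line sits under the outside-the-home condition |
| Unpaid, family farm or business away from home | Working | Yes, on the unpaid line |
| Volunteer | Not listed as working | Yes, on the same unpaid line |
| Housework only | Not working | No |

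The definitions disagree on home-only earners and on volunteers. Volunteers can be told apart from paid workers by the separate lines, but not from unpaid family farm or business workers.

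**Step 2. What the costing needs.** Section 9.2.4 gives no explicit formula. The form's items imply:

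lost-work cost = (full days lost × hours per day × wage) + (part-time days × hours reduced × wage)

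For a home-only earner who answered No:

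- full days lost: asked of everyone, though worded as going to work;
- hours per day: skipped;
- part-time days and hours reduced: asked of everyone;
- wage: the national mean, so no patient data are needed.

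Only the first term cannot be computed. Her wages-lost answer is in dollars, but that is not the valuation section 9.2.4 specifies. The item on hours per treatment visit is open to all, so treatment and travel time is unaffected.

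**Step 3. Effect on the comparison.** Let A and B be the true lost-work costs in the trial and comparison groups, and f_T and f_C the shares of each that cannot be costed.

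observed difference = (1 − f_T)A − (1 − f_C)B = (A − B) − (f_T·A − f_C·B)

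- If f_T = f_C = f, the difference shrinks to (1 − f)(A − B). No difference is created where none exists.
- If the shares differ, the difference can move either way.

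Neither f_T nor f_C can be derived from the documents.

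**Step 4. How many forms could be touched (assumption only).** If 5%, 10% or 20% of patients earned solely at home and all read the question literally:

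- trial patients: 102 × 0.05 = 5.1; 102 × 0.10 = 10.2; 102 × 0.20 = 20.4;
- comparators: 45 × 0.05 = 2.25; 45 × 0.10 = 4.5; 45 × 0.20 = 9.

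These count forms at risk of misclassification. They do not measure cost bias.

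**The case against.** The literal reading is the worst case. Many people take work outside the home to mean employment as opposed to housework, which is the exclusion in section 8.4. Anyone who did some work elsewhere answers Yes, and both groups complete the same form. All of this stands, and it limits the number of patients affected. It does not make the form agree with the protocol.

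Four stronger readings are tempting, and the documents do not support them.

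- *A home worker's losses disappear.* They do not: absence, reduced hours and lost wages are asked of everyone. What is missing is hours per day for full days lost, and an analyst could fill that with a standard working day. The plan does not provide for this.
- *Volunteers are counted as earners and their missed days are paid at the mean wage.* Paid and unpaid work have separate lines, and section 9.2.4 does not say whose missed days are valued.
- *The matching is distorted.* Section 8.4 names no source or categories for employment status, and nothing says the opening answer is the matching variable.
- *The bias can be stated as a percentage or dollar amount.* That would need employment rates, home-working shares, days lost, hours and wages. The documents give none of these, and a between-group error also needs the home-working shares, or the losses attached to them, to differ.

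**Conclusion.** The mismatch is real and its consequence is narrow. On a literal reading, a patient who earned only at home is recorded as not working, contrary to section 8.4, and her full days lost cannot be converted to hours from the data collected. Unpaid family farm or business work, which section 8.4 counts, cannot be separated by work-type line from volunteering, which it does not list.

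The lost-work cost is therefore affected in part. An effect on matching is possible but not shown; what can be said is that the protocol leaves the matching variable undefined. The size of any bias cannot be given from the documents. The conclusion rests on some patients earning only at home and reading the question as written.

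Severity is low. This is one component of a secondary cost-effectiveness analysis that section 9.2.4 describes as exploratory in intent, and the primary endpoint and sample size are untouched. It is still worth correcting, because the change is small and makes the form collect what the protocol says it collects.

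**What to change.** 1. Replace the opening question with the section 8.4 definition, for example: *Before your breast cancer diagnosis, did you hold a paid job or run a business, wherever the work was done (including at home), or help in a family farm or business, paid or not? Please leave out housework and volunteering.*
2. Make the days, hours and occupation items depend on that answer.
3. Give unpaid family farm or business work its own line. If volunteering is recorded at all, put it on a separate line that does not count towards work status.
4. Reword the two absence items to *unable to work* and *worked reduced hours*.
5. State in section 8.4 that this item defines employment status for matching. The survey is completed 2 to 8 weeks after radiation, so also say whether comparators are asked this item when approached or matched after the survey is returned.
6. For completed forms, query any No to the opening question that also reports lost days, reduced hours or lost wages.

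The cost is IRB approval of one revised form, a matching sentence in the protocol, and a short data check. Some completed forms will need recoding, and a few may stay unclassifiable.
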